3.4 Interventions, Administration, and Duration

The intervention period will be 9-months in length for all participants.

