4.2.2 Enrollment, Baseline, and/or Randomization

Enrollment

This study involves a randomized trial with 286 clinicians to inform the best approaches to patient assessments for opioid at clinical visits. Long-term opioid recipients complete the Current Opioid Misuse Measure as standard clinical practice. PainTracker will appear as part of these required assessments randomly for half the patients of clinicians randomized to the intervention (COMM+PainTracker). If a waiver is granted, enrollment date (RCT implementation date) will be recorded for each clinic.

Assessments

Baseline: At baseline, we will assess clinician baseline prescribing monthly morphine milligram equivalents (MMEs), ICD-10 codes, and ordering data.

Enrollment and Randomization (Day 1). Demographics, inclusion/exclusion criteria, ICD-10 codes, and ordering data.

Intervention start (Month 1). ICD-10 codes, and ordering data, Pain Tracker/COMM completion rates, Referral rates to non-opioid care, adverse events

Continuously measured or monitored. ICD-10 codes, and ordering data, Pain Tracker/COMM completion rates, Clinician

monthly MMEs, Referral rates to non-opioid care, adverse events

Intervention end (Month 9): ICD-10 codes, and ordering data, Pain Tracker/COMM completion rates, Referral rates to non-opioid care, adverse events

Follow-up (Month 10-12): ICD-10 codes, ordering data, Clinician MMEs, Referral rates to non-opioid care.

Randomization

We will use cluster randomization at the physician level to avoid contamination that might occur if individual providers are randomized to multiple interventions. We will carry out block randomization of physicians with respect to historical referral rate (high vs. low) by using a random permutation of physician lists in the statistical computing language R. Patients of clinicians in the first half of the permuted list will receive the PainTracker survey intervention in addition to COMM. The second half will receive the control condition (COMM standard clinical practice). The same intervention (PainTracker survey) will be implemented throughout the 9 month study period. No intervention will occur during the 3 month follow-up period; it will be for outcomes assessment only.

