7.4 Data Analyses

For inferential analysis, our *primary hypothesis* is that the proportion of non-opioid referrals will be greater among physicians treating patients who receive PainTracker. We evaluate this with a zero-inflated Poisson model to estimate the number of referrals to non-opioid related care which is then divided by the average number of referrals for each group to estimate the proportion. Our *secondary hypothesis* is that milligram morphine equivalent dose will decrease for persons on high doses of opioid therapy receiving PainTracker. We assume a linear mixed-effects hierarchical knotted spline regression model which offers a flexible way to accommodate non-linear trends before and after the introduction of the intervention.²⁰ This model places a knot at the intervention start date allowing slopes before and during treatment to vary for intervention and control. For our two-group study evaluating this outcome, monthly mean milligram morphine daily dose prescribed for intervention and control, we will place a knot at t^* , the start of the intervention, and evaluate for each comparison between groups:

$$Y = \beta_1 + \beta_2 \text{Time} + \beta_3(\text{Time} - t^*)_+ + \beta_4 \text{Group} + \beta_5 \text{Time} \times \text{Group} + \beta_6(\text{Time} - t^*)_+ \times \text{Group} + \eta + \text{error} \quad [1]$$

where $(z)_+$ is a truncated line function that equals z when z is positive and is equal to zero otherwise, and η is the clinic random effect.

8. **DATA COLLECTION AND QUALITY ASSURANCE**

8.1 **Data Collection Forms**

Data will be collected from electronic medical and billing records and completion rates of PainTracker and COMM surveys.

8.2 **Data Management**

Each of the participating sites will create an extract from their Electronic Medical or Billing Records of the Data Elements. These records will be transferred to the coordinating center as a one time HIPAA compliant limited data set at the end of the study. The CC has created programs and quality control queries for transforming all of the data into a standard model (Observational Medical Outcomes Partnership Common Data Model, version 5.3.1).

The electronic data system, Epic, will have native data capture formats.

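### The morphine-equivalent spline in 7.4 leaves its test contrast and baseline window unstated; the natural test, a difference in slope change, is a weak test of whether dose falls

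*Combined protocol and SAP*

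**What the plan says.** The secondary hypothesis in 7.4 concerns dose: "milligram morphine equivalent dose will decrease for persons on high doses of opioid therapy receiving PainTracker". It does not say whether the fall should be immediate or gradual. The outcome in 7.3.2 is a clinician's monthly dose total, not a rate of change.

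Model [1] in 7.4 contains Time, (Time - t*)+, Group and the products of Group with both time terms. The function (z)+ "is a truncated line function that equals z when z is positive and is equal to zero otherwise". Of the knot the plan says: "This model places a knot at the intervention start date allowing slopes before and during treatment to vary for intervention and control". It mentions no change in level at t*. The random part is a single intercept: "η is the clinic random effect".

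The model is offered to "evaluate for each comparison between groups", and no coefficient or contrast is named. Section 4.2.2 lists baseline monthly MME but not how many months of it. On duration, 3.4 says: "The intervention period will be 9-months in length for all participants". Section 4.2.2 adds MME data for months 10-12. On allocation it says: "We will use cluster randomization at the physician level".

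**The concern.** Because (z)+ is zero at the knot, each arm's fitted line is continuous at t*. The model cannot show a jump there, and beta6 is the only group term that starts at t*. A test of beta6 asks whether the slopes change differently, whereas the hypothesis asks whether dose is lower.

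The model also leaves the pre-start group terms free (beta4 for Group, beta5 for Time x Group), although randomisation makes the true pre-start differences zero in expectation. If dose falls early and stays down, the least-squares line can absorb the fall by tilting beta5. A real reduction in opioid dose could then go undetected, and part of it would look like a trend difference that existed before the intervention.

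**Working it through.** **No figure to reproduce.** The sample-size calculation in 7.1 covers referrals only. The documents give no effect size, SD or power for MME.

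**Inputs.**
- From the documents: 286 clinicians (section 3 and 4.2.2), taken as 143 per arm, and 9 intervention months (3.4). Two-sided alpha of 0.05 is stated in 7.1 for referrals and assumed here for MME.
- Assumed: total SD 1, clinician share of variance 0.6, residuals independent or AR(1) with correlation 0.5, correct standard errors, no clinician-specific trends, 6 to 24 baseline months, knot midway between the last baseline month and the first intervention month.
- The number of clinicians cancels, because effects are scaled to a benchmark test.

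**Step 1: an immediate sustained drop with 9 months before and 9 after.** Put t = -8.5, ..., 8.5 with t* = 0. Since (t)+ = (t + |t|)/2, fitting {1, t, (t)+} is the same as fitting {1, t, |t|}, and beta6 is twice the coefficient of |t|. A unit step is 1/2 + sign(t)/2. The sign function is odd and |t| is even, so over equal windows they are orthogonal. The expected beta6 is therefore exactly 0, whatever the size of the drop. The drop goes into the pre-start slope: beta5 = -(sum of positive t)/(sum of t squared) = -40.5/484.5 = -0.084 per month.

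With unequal windows (independent residuals) a unit drop gives beta6 = +0.085 at 6 baseline months (wrong sign), -0.042 at 12 and -0.105 at 24.

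**Step 2: the benchmark.** This is the difference in mean dose over months 1-9, adjusted for the baseline mean. With 9 baseline months and independent residuals:
- Variance of a 9-month mean: 0.6 + 0.4/9 = 0.644. Covariance of the pre and post means: 0.6.
- SE = sqrt[(2/143)(0.644 - 0.36/0.644)] = sqrt[(2/143)(0.0858)] = 0.0346.
- Mean difference giving 80% power: 2.80 x 0.0346 = 0.097 SD.

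**Step 3: beta6 for the model's own shape, a linear decline over 9 months.** To average 0.097 SD over months 1-9, the decline must reach 0.194 SD, so beta6 = -0.194/9 = -0.0216 per month. The sum of squares of |t| about its mean is 120, so SE(beta6) = 2 x sqrt[(2/143)(0.4/120)] = 0.0137. The ratio is 1.58 and power is Phi(1.58 - 1.96) = 35%.

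**Step 4: all cases.** Power of beta6 when the benchmark has 80% (independent residuals / AR(1) 0.5; ramps evaluated at mid-month):

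| Shape of drop | 6 baseline months | 9 | 12 | 24 |
|---|---|---|---|---|
| Immediate, sustained | 8% / 7% (wrong sign) | 5% / 5% | 6% / 6% | 20% / 17% |
| Phased in over 3 months | 6% / 7% | 11% / 12% | 18% / 17% | 39% / 37% |
| Phased in over 6 months | 16% / 16% | 26% / 26% | 35% / 34% | 57% / 56% |
| Linear over 9 months | 24% / 27% | 35% / 39% | 44% / 49% | 65% / 70% |

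Coding ramps at month end lowers the figures: the 3-month row becomes 5%, 8%, 12-13% and 29-33%. A simulation of 286 clinicians (9 + 9 months, 4,000 replicates) agrees. A sustained drop of 0.145 SD was detected in 4.8% of runs by beta6 and in 78.8% by the adjusted mean; under no effect the rates were 4.95% and 4.6%.

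**The case against.** The strongest reply is that 7.4 never says beta6 is the test. From the same unchanged model one could take the fitted post-start minus pre-start group difference, which combines beta5 and beta6. On the same assumptions, across 6 to 24 baseline months, that contrast has about 58-68% power for an immediate drop, 71-80% for a 3-month phase-in and 88-91% for a linear decline. The last figure beats the 80% benchmark.

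This stands: the near-zero power belongs to a beta6 test, not to the model. A reader might infer that model [1] can test only a slope change and cannot see a fall in dose, but the documents do not support that. The alternative contrast is not in the plan either, and it counts a pre-start slope difference as treatment effect. With a step and 9 + 9 months it recovers 9 x 0.084, about 0.75 of the true drop.

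It is also fair that exactly zero expectation needs an immediate full effect and equal windows, and that the wrong sign needs a baseline shorter than the post-start period. The plan states no baseline length. Surveys go out monthly and are seen at the next visit (3.5), so some phasing-in is likely. The phased rows are therefore the more relevant ones, and beta6 falls short of 80% in all of them.

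Finally, this is a secondary outcome with no power claim.

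**Conclusion.** The point holds in this form: the tested contrast and the baseline window are unspecified, and the natural choice of contrast, beta6, is poorly matched to a hypothesis about dose. If beta6 is used, power is about 5-8% for an immediate drop with 6 to 12 baseline months and 17-20% with 24. It is about 6-39% for a 3-month phase-in, 16-57% for a 6-month phase-in and 24-70% for a linear decline, against 80% for the adjusted mean.

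The algebra (no level term, zero expectation for a step with equal windows) is certain. The power figures depend on the assumed variance share, residual correlation, baseline length and effect shape; they show the order of the loss rather than predict it for this trial.

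A reader might also infer that the benzodiazepine outcome shares the problem. Section 7.3.2 says only that it is handled in a similar way, in the context of the dose calculation, and names no model for it.

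**What to change.** In 7.4, name as the test of the secondary hypothesis the between-arm difference in clinician mean monthly MME over months 1-9, adjusted for that clinician's pre-intervention mean MME. State how many pre-intervention months are used. Keep model [1] to describe the time trend. Apply the same change to benzodiazepines only if they are to be analysed with this model.

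Do not rely on adding a level term and testing level and slope jointly. On the assumptions above, that joint test has 21-47% power for an immediate drop. With 9 + 9 months it has 13-14% for a 3-month phase-in (beta6 alone: 11-12%) and 27-30% for a linear decline (beta6 alone: 35-39%). In a separate check, the added level coefficient had about 36% power where a plain level contrast had 90%.

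The change costs SAP wording only and uses the same data. The averaged contrast does not describe the time course, which the spline can still show. It could lose ground to a slope test if clinicians' own trends varied strongly, although with random slopes up to 0.6 SD per 12 months it still had more power in every case tried with 9 or 12 baseline months.

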3.3 Study Enrollment Procedures

We will seek a waiver of consent for clinician and patient participation. All clinicians treating patients who meet the inclusion criteria in participating practices will be contacted by email to inform them that their patients will be receiving the following assessments: COMM or COMM+PainTracker, depending on clinician study arm assignment.

The COMM is already being delivered as part of standard clinical care. Our study proposes to randomize half of the patients to also receive the PainTracker, which poses no additional risk.

We are requesting a waiver of consent under the Common Rule. The Common Rule (§46.116) specifies that informed consent can be waived when: “(1) The research involves no more than minimal risk to the subjects; (2) The research could not practicably be carried out without the requested waiver or alteration; (3) If the research involves using identifiable private information, the research could not be practicably carried out without the identifiable information; (4) The waiver or alteration will not adversely affect the rights and welfare of the subjects; [and] (5) Whenever appropriate, the subjects will be provided with additional pertinent information after participation.”

Withdrawal of subjects: Patients receive COMM as part of their standard of care at Northwestern Medicine. Patients will not be required to respond to the additional PainTracker surveys, and will continue to receive the same standard of care. After the 9 month intervention, PainTracker surveys will no longer be delivered to patients.

STUDY INTERVENTIONS

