3.5 Handling of Study Interventions

The following study arms will be compared:

Condition 1 (COMM) - On a monthly basis, as part of standard clinical care, patients will receive the Current Opioid Misuse Measure, a 17-item self-report screener to identify and monitor the risk of aberrant opioid-related behavior in chronic pain patients on opioid therapy. The COMM asks patients to report their behaviors over the past 30 days using a five-point Likert-type rating scale. Multiple studies have shown that the COMM can accurately identify patients who are engaging in aberrant opioid-related behavior (defined as medication misuse, abuse, addiction, diversion, and opioid-seeking behaviors) with approximately 80% accuracy. Much of its classification accuracy is because many of the items, while predictive of opioid misuse, do not appear to patients to be asking about opioid misuse.

Condition 2 (COMM+PainTracker) - On a monthly basis, patients will receive both the Current Opioid Misuse Measure (described above) and PainTracker. The latter tracks multiple outcomes relevant to the treatment of chronic pain: pain severity, general activity interference, enjoyment of life interference, sleep (initiating and maintaining), depression, and anxiety. New and returning patients are asked to complete the PainTracker assessment at least one week prior to their appointment.

COMM and PainTracker surveys will be delivered through the patient portal and survey responses will be recorded in the patient electronic health record, and will be visible to the patient's doctor at the time of their next visit. USC will not receive patient survey data, only completion rates.

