7.3 Outcomes

7.3.1 Primary outcome

The primary outcome is the referral rate to non-opioid related care. This includes: mental health, physical therapy and sleep medicine referrals. We will also measure the rate of new starts on antidepressants.

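### The MME spline has no term for the end of treatment at month 9, so if months 10–12 enter the fit, β6 is not the on-treatment slope difference; the window for the referral rate is also unstated.

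*Combined protocol and SAP*

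**What the plan says.** Section 3.4 fixes the length of treatment: "The intervention period will be 9-months in length for all participants". Section 3.3 says what then stops: "After the 9 month intervention, PainTracker surveys will no longer be delivered to patients". Section 4.2.2 adds three further months: "No intervention will occur during the 3 month follow-up period; it will be for outcomes assessment only". The data scheduled for that period are "Follow-up (Month 10-12): ICD-10 codes, ordering data, Clinician MMEs, Referral rates to non-opioid care", and the table in Section 4.1 agrees.

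For the secondary MME outcome, Section 7.4 describes the spline thus: "This model places a knot at the intervention start date allowing slopes before and during treatment to vary for intervention and control". Equation [1] contains Time, (Time − t*)+, Group and the Group products. It has no upper limit on Time and no term at month 9.

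For the primary outcome, Section 7.3.1 says "The primary outcome is the referral rate to non-opioid related care" and names the referral types but no period. Section 7.4 gives the model: "We evaluate this with a zero-inflated Poisson model to estimate the number of referrals to non-opioid related care". No window, period term or exposure term is attached to it.

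**The concern.** The text calls the post-start slope a slope during treatment, but (Time − t*)+ goes on rising after treatment ends. Fitted to every scheduled month, the model puts nine months with PainTracker and three without it on one straight line per arm. β6, the arm difference in the change of slope at t*, carries the secondary hypothesis. If the gap between arms levels off or closes once PainTracker stops, β6 mixes the on-treatment effect with what follows, and a real effect could be understated or missed.

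For the referral rate the matter is simpler. Months 1–9 and months 1–12 are both defensible windows for a primary outcome, and the plan does not choose between them.

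**Working it through.** **MME spline.** The plan gives no figure for this outcome, so there is none to reproduce.

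From the documents: 9 months on treatment, 3 months off, one knot at t*. Assumed: baseline length of 6, 12 or 24 months; equal pre-start slopes in the arms; an arm gap growing by δ per month to month 9. Linear growth from t* is the pattern the model itself presumes, since it has no level-change term.

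Set t* = 0. The arm contrast in equation [1] is D(t) = β4 + β5·t + β6·(t)+. With balanced monthly data and a random intercept, the estimate of β6 is the least-squares fit of the true gap on {1, t, (t)+}.

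With months coded at their ends, the true gap at months 10, 11 and 12 is:
- still growing: 10δ, 11δ, 12δ;
- plateau: 9δ, 9δ, 9δ;
- full return by month 12: 6δ, 3δ, 0.

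Share of δ recovered by single-knot β6, with standard-error (SE) ratios for independent errors:

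| Baseline | Month coding | Plateau | Full return | SE, two knots ÷ one knot | SE, two knots ÷ months 1–9 only |
|---|---|---|---|---|---|
| 6 | end | 0.71 | −0.16 | 1.13 | 0.98 |
| 6 | middle | 0.77 | 0.09 | 1.13 | 0.96 |
| 12 | end | 0.81 | 0.22 | 1.20 | 0.97 |
| 12 | middle | 0.84 | 0.38 | 1.19 | 0.95 |
| 24 | end | 0.85 | 0.41 | 1.28 | 0.96 |
| 24 | middle | 0.88 | 0.52 | 1.26 | 0.93 |

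If the gap keeps growing, the share is 1.00 in every row. With (t − 9)+ added it is 1.00 in every row and every case; the same holds if the fit stops at month 9.

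A hand check: against continued growth, the shortfall at months 10–12 is δ, 2δ, 3δ under the plateau and 4δ, 8δ, 12δ under full return, exactly four times as much. β6 is linear in the data, so its loss must also be four times as large. For 12 months, end-coded: 1 − 0.806 = 0.194, and 1 − 4 × 0.194 = 0.22, as tabulated.

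**Referral rate.** First the plan's own figure (Section 7.1). The design effect is 1 + (17 − 1) × 0.06 = 1.96, and the effective number per arm is 150 × 17 / 1.96 = 2,550 / 1.96 = 1,301. At 80% power and two-sided 0.05 (unpooled normal approximation), the detectable difference is 2.67 points at a 5% baseline and 3.54 points at 10%. These match the stated 3% and 4% once rounded up; power at exactly 3 and 4 points is 87–88%.

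Now read 5% versus 8% as nine-month proportions (87% power), and let a share f of the effect persist in months 10–12.

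- *Accumulated over 12 months.* Control: 5% × 12/9 = 6.67%. Intervention: 8% + (5% + 3% × f) × 3/9.
  - f = 0: 9.67%, difference 3.0 points, power 80%.
  - f = 0.5: 10.17%, difference 3.5 points, power 90%.
  - f = 1: 10.67%, difference 4.0 points, power 95%.
- *Average rate over 12 months.* The difference is 3 × (9 + 3f)/12 points.
  - f = 0: 2.25 points, power 67%.
  - f = 0.5: 2.6 points, power 79%.
  - f = 1: 3.0 points, power 87%.

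At f = 0 the rate ratio falls from 8/5 = 1.60 to 9.67/6.67 = 1.45. So pooling can raise or lower power relative to months 1–9, depending on f and on the metric. The two-proportion test stands in here for the zero-inflated Poisson model.

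**The case against.** The best defence is the plan's own phrase about slopes before and during treatment. Treatment lasts nine months, so the fit may be meant to end at month 9, in which case equation [1] is adequate. Collecting data in months 10–12 does not mean pooling them. This stands as far as it goes: the documents do not say the months are pooled. But the sentence before it speaks of trends before and after the intervention is introduced, the equation sets no upper limit on Time, and outcome assessment is the only stated purpose of follow-up. If the phrase is a restriction, the follow-up MMEs have no planned analysis.

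A reader might infer that both effects are diluted under the plan as written. The documents do not support that. Pooling is not stated, and loss of effect after month 9 is an assumption. Section 3.5 says responses are visible to the patient's "doctor at the time of their next visit", so late surveys could still prompt action in months 10–12. For referrals, accumulated power with half the effect persisting (90%) exceeds that for months 1–9 (87%).

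A reader might also infer that patients get no survey in months 10–12. Section 3.3 says only that PainTracker stops; COMM is standard care and is not said to stop.

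Finally, the spline figures move with baseline length and month coding, so they should be read as ranges.

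**Conclusion.** The point holds conditionally for the MME spline. Equation [1] cannot separate months 1–9 from months 10–12. If the later months are fitted, β6 recovers about 0.71–0.88 of the on-treatment slope difference under a plateau, about −0.16 to 0.52 under full return by month 12, and 1.00 under continued growth. The sign can reverse with a short baseline and full return. These ranges rest on linear growth to month 9, a baseline of 6 to 24 months, equal pre-start slopes and balanced monthly data.

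For the primary referral rate, what is established is an unstated analysis window. A loss of power or effect there is possible but not shown.

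**What to change.** Add (Time − t* − 9)+ and its product with Group to equation [1]. Test β6 as the arm difference in slope for months 1–9, and report the month 10–12 change as persistence. State the length of the baseline series and how months are coded.

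The cost is SAP wording and two model terms; no new data are needed. The standard error of β6 rises by about 13–28% over the single-knot 12-month fit, but is 2–7% below that from dropping months 10–12. Those ratios assume independent errors around a random intercept; serial correlation would change them. Ending the fit at month 9 is a defensible alternative if the plan says so.

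As a secondary clarification, state the window for the primary referral rate, for example months 1–9 with months 10–12 reported separately, and whether it is an accumulated count or a rate per month. This costs one or two sentences.

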7.3.2 Secondary outcomes

Secondary outcomes include: 1) clinician aggregate monthly milligram (mg) morphine equivalent (ME) and 2) benzodiazepine prescribing. We will estimate the daily milligram morphine equivalent for each clinician by summing the total number of daily morphine equivalents written within a monthly observation period divided by the number of 30 days. For example, suppose a clinician has three qualifying visits over three days in one month and prescribed as follows: Patient #1 is prescribed 200mg ME/day x 30 days, Patient #2 has tapered from 200 mg ME/day to now 100mg ME/day x 30 days and Patient # 3 is on a tapering plan from 60 to 30 mg ME/day and receives 50 mg ME/day x 15 days. The clinician's outcome for that month then equals:

$$\begin{aligned} & [(200 \text{ mg/day} \times 30 \text{ days}) + 100 \text{ mg/day} \times 30 \text{ days}) + (50 \text{ mg/day} \times 15 \text{ days})] \times [1 \text{ Month}/30 \text{ days}] \\ & = (300 \text{ mg} \times 1 + 100 \text{ mg} \times 1 + 50 \text{ mg} \times (\frac{1}{2})) = 425 \text{ mg MED}/[\text{Month}]. \end{aligned}$$

Oral buprenorphine will be excluded from the calculations as it relates to opioid use disorder treatment. Morphine equivalent dose will be computed by standard means described elsewhere.²⁸ Benzodiazepines will be handled similarly to monthly milligram morphine equivalents but with valium morphine equivalents. Qualifying pain visits will be captured by including all ICD-10 pain diagnostic codes and excluding active cancer diagnoses.

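### The MME model puts its only random effect on clinic, while randomisation and outcome are per clinician with repeated months, so the standard error of β6 is generally wrong, in an unknown direction

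*Combined protocol and SAP*

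**What the plan says.** - **Allocation.** Section 4.2.2: "We will use cluster randomization at the physician level". Physicians are blocked on historical referral rate; clinic plays no part in the allocation.
- **Outcome.** Section 7.3.2: "We will estimate the daily milligram morphine equivalent for each clinician", with one value per monthly observation period.
- **Model.** Section 7.4: "We assume a linear mixed-effects hierarchical knotted spline regression model". Equation [1] has fixed effects for time, time after the knot t*, group and their interactions, plus η and an error term. Of η it says only that it "is the clinic random effect". The documents name no clinician effect, clinician slope, residual correlation or robust SE.
- **Knot.** Section 7.4: "This model places a knot at the intervention start date allowing slopes before and during treatment to vary for intervention and control". The group difference in slope change is β6, although the text does not name it as the tested contrast.
- **Follow-up.** Clinician MMEs are also collected in months 10–12, and Section 4.2.2 says: "No intervention will occur during the 3 month follow-up period". Section 7.4 does not say whether those months enter the fit.

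**The concern.** Taken as written, equation [1] treats all months from one clinician as independent, given the clinic. A clinician's aggregate MME depends on panel size and case mix. One would therefore expect stable differences between clinicians and carry-over from month to month. The model represents neither.

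The two omissions pull the SE of β6 in opposite directions. Stable clinician differences go into the residual and inflate the model SE, although β6 is a within-clinician contrast that those differences do not touch; power is lost. Serial correlation makes the true SE larger than the model believes, so the test rejects too often. The test of the stated secondary hypothesis thus has a size that nobody can state in advance.

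A smaller, conditional question sits beside this. With a single knot, any months 10–12 in the fit would share the treatment-period slope.

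**Working it through.** **Stated figure.** There is none to reproduce. The intraclass correlation of 0.06 and the power statement in Section 7.1 concern the referral outcome; no variance or power is given for MME.

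**Inputs.**
- From the documents: 286 clinicians, 9 intervention months, 3 follow-up months. Two-sided 5% is stated for the referral outcome and used here too.
- Assumed: 143 clinicians per arm, 6 or 12 baseline months, total clinician-month variance within clinic of 1, a share s of it in a stable clinician intercept, and the rest independent or AR(1) with correlation ρ.

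**Formulas.** For one clinician let Z have rows [1, t, t₊], with t measured from t*, let A = (Z′Z)⁻¹Z′, and let V be the true covariance of that clinician's months.
- True Var(β6) = (4/286)·[AVA′]₃₃
- Model Var(β6), clinic intercept plus independent error = (4/286)·σ²·g, with σ² = 1 and g = [(Z′Z)⁻¹]₃₃
- Actual alpha = 2{1 − Φ(1.96 × ratio)}, with ratio = model SE / true SE

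**Step 1: clinician intercept, independent months.** A stable intercept drops out of the slope change, so [AVA′]₃₃ = (1 − s)g and the ratio is 1/√(1 − s), whatever the number of months.
- s = 0.5: 1/√0.5 = 1.41; 1.96 × 1.41 = 2.77; alpha 0.6%
- s = 0.8: 1/√0.2 = 2.24; 1.96 × 2.24 = 4.38; alpha under 0.1%

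**Step 2: add AR(1).** The ratio becomes r₀(ρ)/√(1 − s), where r₀ is the ratio at s = 0. With time coded at mid-month:

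| Baseline months | ρ | s = 0: ratio (alpha) | s = 0.5 | s = 0.8 |
|---|---|---|---|---|
| 12 | 0.5 | 0.67 (19%) | 0.95 (6.2%) | 1.50 (0.3%) |
| 12 | 0.8 | 0.61 (23%) | 0.87 (9.0%) | 1.37 (0.7%) |
| 6 | 0.5 | 0.73 (15%) | 1.03 (4.3%) | 1.63 (0.1%) |
| 6 | 0.8 | 0.77 (13%) | 1.09 (3.3%) | 1.72 (0.1%) |

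Coding time at the start or end of the month as well widens the s = 0.5 and 0.8 columns slightly, to 0.86–1.75, and puts alpha at 12–23% for ρ = 0.8 with s = 0. The error passes through zero: with 12 baseline months and ρ = 0.8 the ratio is 1 at s = 1 − 0.612² ≈ 0.63.

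**Step 3: check by simulation.** Fitting the clinic-intercept mixed model to simulated data (20 clinics assumed, 12 baseline months) gave 1.40 for s = 0.5 with independent months (200 runs, alpha 0.5%) and 0.82 with ρ = 0.8 added (60 runs, alpha 13%). The direction agrees; the second run is small.

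**Step 4: would a clinician intercept alone suffice?** With independent months, yes (ratio 1.00). With ρ = 0.5 / 0.8 the ratio is 0.64 / 0.51 for 12 baseline months (alpha 21% / 32%) and 0.68 / 0.60 for 6 (alpha 18% / 24%). Moving the intercept without dealing with serial correlation can make over-rejection worse.

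**Step 5: months 10–12, if included.** I fitted [1, t, t₊] by least squares to a group difference that rises linearly for 9 months and then stays flat, or falls to zero by month 12. Over 6 or 12 baseline months and start-, mid- or end-of-month coding, the fitted β6 is 71–89% of the truth for the plateau and −16% to 55% for the fade. With 12 baseline months and mid-month coding it is 84% and 38%.

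**The case against.** - **Clinic may be a slip for clinician.** Quite possible, and the sponsor should confirm. It would remove the error in Step 1 but leave serial correlation and clinician slopes unspecified, which is the situation in Step 4.
- **Independent errors are a reading.** Equation [1] says only error. That stands, but a plan that leaves the residual structure open does not settle the SE either.
- **The unit of Y is not fully clear.** Section 7.3.2 supports clinician-months. Section 7.4 speaks of a monthly mean for each group and of persons on high doses. The unit should be stated; repeated measures on the randomised clinician remain either way.
- **Large false-positive rates.** A reader might infer that the model over-rejects badly, at 23% for example. That needs strong serial correlation with no stable clinician differences. With both present, the figures run from mild inflation to marked conservatism.
- **Months 10–12.** Section 7.4 speaks of slopes before and during treatment, which suggests that follow-up months are left out. The documents do not show that they are included, so no attenuation can be asserted, and its size depends strongly on time coding and baseline length.
- **Benzodiazepines.** A reader might extend the point to them. The sentence in Section 7.3.2 that likens them to MME concerns how the measure is built; no model for them is written.

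**Conclusion.** The point holds for the secondary MME outcome. Equation [1] omits the clinician, who is both the randomised unit and the unit measured repeatedly, so its model-based SE for β6 is right only if there is neither clinician variance nor serial correlation, or if the two happen to cancel.

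The level mismatch rests on the documents alone. The sizes rest on assumed variance components, baseline length and equal arms:
- stable clinician differences only: model SE 1.41 to 2.24 times the true SE for shares of 50% to 80%;
- the same shares with AR(1) of 0.5–0.8: 0.86 to 1.75 times, alpha about 9% down to 0.1%;
- AR(1) of 0.8 with no clinician intercept: alpha about 12–23%, an extreme case.

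The documents support neither a fixed direction nor any effect on the primary referral analysis, which uses a different model. That clinicians of both arms share clinics is likely under physician-level allocation but not stated, and the result does not need it. The correction should be made before analysis.

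**What to change.** In Section 7.4:
1. Confirm whether η was meant for clinic or clinician, and state the unit of Y.
2. Replace η with a clinician random intercept; clinic may stay as a level above it.
3. Add clinician-clustered robust SEs, or clinician random slopes (time and time after t*) with a serial residual structure such as AR(1). The intercept alone is not enough.
4. Name β6 as the tested contrast and give the number of baseline months and the time coding.
5. State that the fit uses months up to 9 only, or add a second knot with its group interaction at the end of month 9.
6. Say which model serves benzodiazepines. If it is equation [1], the same changes apply.

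The cost is SAP wording and a slightly larger model, with no new data.
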